6.2. Secondary and Exploratory Efficacy Endpoints

The **secondary efficacy** endpoints are the following:

- Total clinical symptom score over time, with special interest to day 6 and 7. The total clinical symptom score is determined as the sum of the scores (grades) of the 13 self-reportable symptoms on the Subject Symptoms Card (SSC).

Note: ‘The symptom scores will be translated into numerical values as follows:

0 = ‘I have No symptom’

1 = ‘just noticeable’

2 = ‘It’s clearly bothersome from time to time, but it doesn’t stop me from participating in activities’

3 = ‘It’s quite bothersome most or all the time and it stops me from participating in activities’

4 = ‘Symptoms at rest’

- The viral load of RSV-A Memphis 37b as determined by quantitative RT-PCR assay of nasal wash samples over time, with special interest on Day 6 and Day 7 post challenge.
- The peak viral load is defined as the maximum viral load as determined by quantitative RT-PCR assay of nasal wash samples, observed over the whole quarantine period.
- The viral load of RSV-A Memphis 37b as determined by quantitative culture of RSV of nasal wash samples and the corresponding AUC, with special interest on Day 6 and Day 7 post challenge. The AUC will be calculated based on equation (1). In case the first timepoint after challenge and/ or last timepoint after challenge is missing, it will be set to zero. No other missing time point will be imputed.

The viral load values from the quantitative culture of RSV (plaque assay) range from 1.70 to 5.90 in log₁₀ PFU/ml. The following imputation rules will be used:

- <1.70 log₁₀ PFU/ml **not detected** -> 0
 - <1.70 log₁₀ PFU/ml **detected** -> 1.70
 - <2.70 log₁₀ PFU/ml **not detected** -> 0
 - <2.70 log₁₀ PFU/ml **detected** -> 2.70
 - >5.90 log₁₀ PFU/ml -> 6.00
 - INVALID -> missing
- Weight of mucus produced over time and the corresponding AUC. The AUC will be calculated based on equation (1). In case the first timepoint after challenge and/ or last time point after challenge is missing, it will be set to zero, no other missing time point will be imputed.
 - Number of tissues used per time point.

- Proportion of subjects with symptomatic RSV infection. Symptomatic RSV infection is defined in two ways:
 - Conservative: the subject has two or more quantifiable RT-PCR measurements on different samples and the subject has one of the following:
 - symptoms from two different categories (Upper Respiratory, Lower Respiratory, Systemic) from the SSC, regardless of grade and assessment timepoint *OR*
 - any Grade 2 symptom from any category.
 - Liberal (RT-PCR): two or more quantifiable RT-PCR measurements plus any clinical symptom of any severity from the SSC.

The SSC categories are defined as follows:

- *Upper Respiratory symptoms*: runny nose, stuffy nose, sneezing, sore throat, earache
- *Lower Respiratory symptoms*: cough, shortness of breath, chest tightness, wheeze
- *Systemic symptoms*: malaise, headache, muscle and/or joint ache, chilliness/feverishness

Note: the quantifiable RT-PCR assessment and the symptoms should not necessarily occur at the same day.

The **exploratory efficacy** endpoints are the following:

- Proportion of subjects with symptomatic RSV infection based on RT-PCR or serology. Symptomatic RSV infection is defined as:
 - Liberal (RT-PCR or Serology): the subject has two or more quantifiable RT-PCR measurements or serology confirmation of RSV (4-fold increase in G a or G b Elisa, 28 days after challenge), and any clinical symptom of any severity.
- AUC of the total clinical symptom score. The AUC for the total clinical symptom score will be calculated based on equation (1). In case the first and/or last time point is missing, it will be set to zero, no other missing time point will be imputed.
- Clinical symptom scores per item over time
- Respiratory parameters measured by spirometry:
 - Forced expiratory volume in 1 second (%) – FEV1
 - Forced vital capacity (%) – FVC
 - FEV1/FVC Ratio (%) – FEV1/FVC

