2. OBJECTIVES, ENDPOINTS, AND HYPOTHESIS

2.1. Objectives and Endpoints

2.1.1. Objectives

Primary Objective

The primary objective is to assess a trend for the prophylactic efficacy of a single dose of 1×10^{11} vp of Ad26.RSV.preF administered intramuscularly to adults aged 18-50 years in the RSV challenge model in terms of reduction of nasal wash viral load as measured by the area under the curve (AUC) over time by quantitative reverse transcriptase-polymerase chain reaction (RT-PCR) compared to placebo.

Secondary Objectives

- To assess a trend for prophylactic efficacy of a single dose of Ad26.RSV.preF in the RSV challenge model in terms of reduction of nasal wash viral load as measured by the peak viral load of the RT-PCR compared to placebo.
- To assess the effect of a single dose of 1×10^{11} vp of Ad26.RSV.preF on viral load, as measured by RT-PCR and quantitative culture of RSV, and clinical symptoms on Day 6 and Day 7 post-challenge compared to placebo.
- To assess a trend for prophylactic efficacy of a single dose of 1×10^{11} vp of Ad26.RSV.preF in the RSV challenge model in terms of prevention of symptomatic RSV infection defined as two quantifiable RT-PCR measurements and one or more positive clinical symptoms of any grade from two different categories in the symptom scoring system (Upper Respiratory, Lower Respiratory, Systemic), or one Grade 2 symptom from any category compared to placebo.
- To assess a trend for prophylactic efficacy of a single dose of 1×10^{11} vp of Ad26.RSV.preF in the RSV challenge model in terms of prevention of symptomatic RSV infection defined as two quantifiable RT-PCR measurements and one or more positive clinical symptoms of any grade in any category from the symptom scoring system compared to placebo.
- To assess a trend for prophylactic efficacy of a single dose of 1×10^{11} vp of Ad26.RSV.preF in the RSV challenge model in terms of the weight of mucous secretions and tissue count over time compared to placebo.
- To assess the safety and tolerability of a single dose of 1×10^{11} vp of Ad26.RSV.preF administered intramuscularly.

Exploratory Objectives

- To assess a trend for prophylactic efficacy of a single dose of 1×10^{11} vp of Ad26.RSV.preF in the RSV challenge model in terms of clinical symptoms as measured by the AUC over time of symptoms collected by a graded symptom scoring system compared to placebo.

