2.1.2. Endpoints

Primary Endpoint: Viral Load

The primary endpoint is the VL-AUC of RSV-A Memphis 37b as determined by quantitative RT-PCR assay of nasal wash samples.

Nasal wash samples are taken every 12 (± 1) hours beginning two days (ie, in the morning) after inoculation of the challenge virus. Quantitative RT-PCR is utilized to measure viral load.

Secondary Endpoints

- Peak viral load of RSV-A Memphis 37b, defined as the maximum viral load as determined by quantitative RT-PCR assay of nasal wash samples, observed over the entire time period.
- Occurrence of symptomatic RSV infection defined as two quantifiable RT-PCR measurements at different timepoints plus symptoms of any grade from two different categories from the subject symptom card (SSC)^a or two quantifiable RT-PCR measurements plus any Grade 2 symptom from any category. The three SSC categories are:
 - Upper Respiratory symptoms: runny nose, stuffy nose, sneezing, sore throat, earache

^a See [Attachment 3](#).

-
- Lower Respiratory symptoms: cough, shortness of breath, chest tightness, wheeze
 - Systemic symptoms: malaise, headache, muscle and/or joint ache, chilliness/feverishness
 - Occurrence of RSV infection defined as two quantifiable RT-PCR measurements plus any clinical symptom of any severity.
 - Total weight of mucus produced and tissue count.
 - Safety and tolerability
 - Unsolicited adverse events (AEs) from ICF signature until 28 days after vaccination, and from the entry into the Unit until 28 days after challenge.
 - Safety data including, but not limited to, physical examinations, vital signs, 12-lead electrocardiograms (ECGs) and clinical laboratory results (including biochemistry, hematology, and urinalysis).
 - Serious adverse events (SAEs) throughout the study (from signing the ICF to the end of the study, 6 months after vaccination).
 - Solicited local and systemic AEs for 7 days after vaccination.

Exploratory Endpoints

- AUC of the total clinical symptom score. The total clinical symptom score is a composite of 13 self-reported symptoms (on the SSC) divided into three categories (Upper Respiratory, Lower Respiratory, Systemic).
- The VL-AUC of RSV-A Memphis 37b, as determined by quantitative culture of RSV of nasal wash samples.

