9.1.5.3. Post-challenge

On each of the 11 days after the challenge, procedures will include a directed physical examination, spirometry and monitoring of vital signs. Nasal wash samples will be taken every 12 (\pm 1) hours from the second day after challenge until discharge. The SSC will be filled out three times a day by the subject and reviewed by the attending physician. Tissue counts and mucus weight will be determined for each 24-hour interval. ECGs will be carried out, and blood samples collected for clinical laboratory tests (cardiac enzymes only) on Days 3, 7 and 11. Any unsolicited AEs/SAEs and concomitant medications will be recorded.

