9.2.3. Mucus Weight and Tissue Count

At several timepoints during the study, as is indicated in the [Time and Events Schedule](#), the mucus weight (nasal) will be assessed.

Subjects will be given pre-weighed packets of paper tissues (handkerchiefs). After each tissue is used for nose blowing or sneezing, the subjects should store them in an airtight plastic bag.

Paper tissue and bag distribution first takes place on Study Day –1 at 08:00 a.m. (\pm 30 minutes). Paper tissue collection starts from Study Day 1 through the day of discharge at approximately the same time.

Subjects will be instructed to place used single tissues into a specified bag which will be collected the following morning. A daily 24-hour collection will take place and new bags will be distributed.

All paper tissues used by each subject will be collected for each 24-hour period throughout the quarantine phase, to determine daily mucus weight and number of tissues used.

Used and unused tissues will be counted. In case of missing tissues, they will be replaced by new dry tissues, and the subjects will be re-educated about proper tissue use and collection.

Collection time of the plastic bags, daily mucus weight, and number of tissues used should be recorded on the eCRF.

Tissues will not be stored after the mucus weight is determined.

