11.4. Efficacy Analyses

For efficacy, baseline is defined as the last assessment challenge with the virus.

The **primary efficacy endpoint** is the VL-AUC of RSV-A Memphis 37b as determined by quantitative RT-PCR assay of nasal wash samples. The VL-AUC is calculated based on the viral load values measured twice daily, starting with the baseline value, and ending with the last available value before discharge.

For this primary efficacy endpoint the exact Wilcoxon Rank Sum test will be performed and the one-sided p-value will be interpreted at the 5% and 20% significance level, specifically only analysing the statistical significance of a reduction in VL-AUC in the active versus placebo groups.

The **secondary efficacy endpoints** are:

- The peak viral load of RSV-A Memphis 37b, defined as the maximum viral load as determined by quantitative RT-PCR assay of nasal wash samples, observed over the entire time period
- The effect of vaccination on viral load and symptoms on Day 6 and Day 7
- The viral load of RSV-A Memphis 37b as determined by quantitative RT-PCR assay of nasal wash samples over time
- The VL-AUC of RSV-A Memphis 37b as determined by quantitative culture of RSV of nasal wash samples and the corresponding AUC
- Weight of mucus produced over time and the corresponding AUC, tissue count
- Proportion of subjects with symptomatic RSV infection. Symptomatic RSV infection is defined in two ways:
 - Conservative: the subject has two or more quantifiable RT-PCR measurements on different samples **and** the subject has one of the following
 - symptoms from two different categories (Upper Respiratory, Lower Respiratory, Systemic) from the SSC, regardless of grade and assessment timepoint.
 - any Grade 2 symptom from any category.
 - Liberal: two or more quantifiable RT-PCR measurements plus any clinical symptom of any severity.

Note: the quantifiable RT-PCR assessment and the symptoms should not necessarily occur at the same day.

Exploratory efficacy endpoints are:

- Proportion of subjects with symptomatic RSV infection (RT-PCR or serology). Symptomatic RSV infection is defined as having two or more quantifiable RT-PCR measurements or serology confirmation of RSV, and any clinical symptom of any severity.
- Total clinical symptom score (using a composite of 10 and 13 self-reported symptoms on the SSC) over time and the corresponding AUC.

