6. EFFICACY

6.1. Primary Efficacy Endpoint

The primary endpoint is the area under the viral load-time curve (VL-AUC in \log_{10} copies/ml) of RSV-A Memphis 37b as determined by quantitative RT-PCR assay of nasal wash samples. Nasal wash samples are taken every 12 (± 1) hours beginning two days (ie, in the morning) after inoculation of the challenge virus. VL-AUC is calculated based on the viral load values measured twice daily, starting with the baseline value, and ending with the last available value before discharge.

In the calculation of the AUC, not only the date, but also the timing (the real hours, minutes and seconds as captured in the database should be used, but the AUC result should be reported in hours), of the assessment, is taken into account:

$$AUC\ VL = \sum_{i=2}^T \frac{[VL_{t_i} + VL_{t_{(i-1)}}]}{2} [t_i - t_{(i-1)}] \quad (1)$$

where

t_i = (actual) timepoint i

t_{i-1} = (actual) timepoint $(i - 1)$

T = last timepoint

t_1 = first timepoint after challenge

VL_{t_i} = \log_{10} viral load at (actual) timepoint i

$VL_{t_{(i-1)}}$ = \log_{10} viral load at (actual) timepoint $(i - 1)$

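### The mucus endpoint is a total in Protocol 2.1.2 and an AUC in Protocol 11.4; the SAP follows the AUC, so no per-subject total of mucus or tissues is ever derived

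*SAP*

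**What the plan says.** The protocol describes this endpoint in two ways. Section 2.1.2, repeated in the synopsis and Attachment 2, lists "Total weight of mucus produced and tissue count". Section 11.4 lists "Weight of mucus produced over time and the corresponding AUC, tissue count". The matching objective in Section 2.1.1 is worded "in terms of the weight of mucous secretions and tissue count over time compared to placebo", which suits a time course at least as well as a total.

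On measurement, Protocol 9.1.5.3 says "Tissue counts and mucus weight will be determined for each 24-hour interval", and Protocol 9.2.3 says "Paper tissue collection starts from Study Day 1 through the day of discharge at approximately the same time". Section 9.1.5.1 instead places the start of the first collection on Day -1 with weighing on Day 0, so a pre-challenge bag may also exist.

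SAP 6.2 takes up the 11.4 version: "Weight of mucus produced over time and the corresponding AUC. The AUC will be calculated based on equation (1"). A missing first or last value becomes zero, and nothing else is imputed. Tissues appear as "Number of tissues used per time point". SAP 6.2.1 tabulates and plots both measures per time point, gives the mucus AUC boxplots and an exact Wilcoxon test, and adds individual profiles of both. No sum over days is derived for either. SAP 2, which records changes to planned analyses, is silent on this endpoint.

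Equation (1), in SAP 6.1, is a trapezoid for log10 viral load at actual clock times, with its first point defined as the "first timepoint after challenge". The text just before it starts the viral-load AUC at baseline.

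**The concern.** A reader of the protocol's endpoint list expects a result in grams per subject and a number of tissues per subject, by group. Neither is planned.

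The substitute for mucus also uses a formula made for another kind of data. A viral load is a level at one moment, and integrating levels over time is sensible. A bag weight is already the integral over its own 24 hours. Applying the trapezoid to it multiplies a total by time, gives half weight to bags at the ends of the series, and makes the result depend on collection times. A subject still secreting at discharge loses half of the last day's output. The listed endpoint would be reported in gram-hours that nobody can read as an amount of mucus, and the tissue endpoint would have no single figure per subject.

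**Working it through.** The documents give no figure for this endpoint, so there is nothing to reproduce. The check applies equation (1) to daily bag weights. The gram values are assumptions; the algebra is not.

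**Inputs.** 24-hour bags at about the same time each day (Protocol 9.1.5.3, 9.2.3); 12 bags, w1 to w12, for collection on Days 1 to 12; equation (1) with actual times, result in hours (SAP 6.1).

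**1. Algebra.** AUC = sum of (w_i + w_(i-1))/2 x (t_i - t_(i-1)). With equal 24-hour spacing:

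- Series starting at the first post-challenge bag: AUC/24 = total - (w1 + w12)/2.
- Series starting at a pre-challenge Day 0 bag w0: AUC/24 = total - w12/2 + w0/2. The first post-challenge bag then counts in full.

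The last bag is halved either way. The mucus item in SAP 6.2 refers to the first time point after challenge, so the first form is the more direct reading, but the baseline wording in SAP 6.1 leaves it open.

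**2. Size of the shortfall.**

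| Assumed course, g per bag | Total | (w1 + w12)/2 | AUC/24 | Shortfall | AUC/24 if an empty Day 0 bag comes first |
|---|---|---|---|---|---|
| Flat, 2 each day | 24.0 | 2.0 | 22.0 | 8.3% | 23.0 |
| Peaked: 0, 0, 0.5, 1, 3, 5, 6, 4, 2, 1, 0.5, 0 | 23.0 | 0 | 23.0 | 0% | 23.0 |
| Early: 3, 4, 5, 3, 2, 1, 0.5, then 0 | 18.5 | 1.5 | 17.0 | 8.1% | 18.5 |
| Late: 0, 0, 0, 0, 0.5, 1, 2, 3, 5, 6, 5, 4 | 26.5 | 2.0 | 24.5 | 7.5% | 24.5 |
| Late-rising, end bags summing to 12.5 | 60.0 | 6.25 | 53.75 | 10.4% | not computed |

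**3. Collection time.** One interior bag h hours late, with the next back on schedule, adds r x h²/2 to the AUC at a constant rate r. For h = 1, 2, 4 and 6 the increase is 0.01%, 0.03%, 0.13% and 0.28%. If the late bag is the peak bag of the peaked course, it is 0.11%, 0.24%, 0.60% and 1.09%. The total is unchanged. A last bag 6 hours late at a constant rate raises the AUC by 3.7% and the total by 2.1%.

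**4. Group comparison.** The factor of 24 cannot alter ranks. In 4,000 simulated trials (22 per arm, 65% infected in both arms, course height halved under vaccine, rank test by normal approximation), power for total against AUC was 29.2% against 29.4% at one-sided 5%, and 61.5% against 61.5% at 20%. The mean Spearman correlation of the two measures was 0.999. These courses peak around Day 6.5, so end bags are mostly small, which favours agreement. Further assumed 22-per-arm simulations gave correlations of at least 0.995 and rejection rates within about 3 percentage points.

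**5. Unweighed and merged bags.** These decide how a sum must be defined.

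- Peaked course with the 6 g Day 7 bag never weighed: the available bags sum to 17.0 against a true 23.0. Adding the adjacent-day mean, (5 + 4)/2 = 4.5, gives 21.5, which is also what the trapezoid gives.
- Flat course with two days in one 4 g bag: AUC/24 rises by (4 + 2)/2 = 3, to 25.0. Summing and also imputing the skipped day gives 20 + 4 + (2 + 4)/2 = 27.0. Counting the bag once gives 20 + 4 = 24.0, the true total.
- Flat course with the last bag missing and set to zero: the sum falls to 24 - 2 = 22.0, so the SAP's end-point rule would remove a whole day from a total.

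**The case against.** The strongest reply is that the SAP does what Protocol 11.4 says. The AUC is named there, and the objective speaks of weight and count over time. The synopsis calls for descriptive analysis of secondary endpoints, and SAP 6.2.1 already urges caution with their p-values. The simulations show almost the same ranking from either measure. All of this stands, and it limits the point.

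Several stronger readings are tempting and are not supported:

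- *That the SAP departs from the protocol.* The split lies inside the protocol, between 2.1.2 with Attachment 2 and 11.4.
- *That tissue count goes unanalysed.* It is tabulated, plotted and profiled. Only a per-subject figure is absent. The protocol does not attach the word total to it unambiguously, and it promised no test.
- *That late collection badly inflates the AUC.* An assumed peaked course of 49.5 g goes from 49.0 to 64.0 (+31%) if the peak day and the next share one 48-hour bag. Protocol 9.2.3 specifies a daily collection during quarantine, and neither document provides for such a bag. For delays of hours the effect is the small one in step 3.
- *That half of the first bag is certainly lost.* That depends on the unresolved start point.
- *That the treatment comparison is biased.* Nothing here shows it.

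What the reply does not answer is that the listed endpoint has no figure in its own units, and that equation (1) does not suit interval totals.

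**Conclusion.** The point holds as a mismatch of endpoint definition together with an ill-suited formula. The algebra is exact for equally spaced bags; the 0 to about 10% range depends on assumed courses and on the start point. The size for inference is small under the assumed simulations, which do not cover a trial where heavy secretion at discharge is common and differs by arm. The case for changing the plan is that readers should get the endpoint the protocol lists, in grams and tissues, and that this is nearly free before database lock.

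**What to change.** In SAP 6.2 and 6.2.1:

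1. Derive per subject the sum of 24-hour mucus weights and the sum of tissues used over a fixed post-challenge window. State which bag is first, settling the difference between Protocol 9.1.5.1 and 9.2.3. A fixed window matters because stays can run past Day 12.
2. Summarise both totals by group with boxplots. Give total mucus weight the exact Wilcoxon test now planned for the mucus AUC, and keep the AUC as supplementary with its start point stated. Report total tissue count descriptively; a test is optional.
3. Use the mean of the adjacent days only for a day whose output was never weighed. Count a bag spanning two days once, with no imputation. Do not set a missing first or last bag to zero; state another rule, for example the neighbouring day's value, and report how many subjects it affects.
4. Align Protocol 2.1.2, 11.4 and Attachment 2 on the same definition.

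The cost is SAP wording, two derived variables, slightly more output and a small protocol alignment. No new data are needed.

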- Peak viral load of RSV-A Memphis 37b, defined as the maximum viral load as determined by quantitative RT-PCR assay of nasal wash samples, observed over the entire time period.
- Occurrence of symptomatic RSV infection defined as two quantifiable RT-PCR measurements at different timepoints plus symptoms of any grade from two different categories from the subject symptom card (SSC) or two quantifiable RT-PCR measurements plus any Grade 2 symptom from any category. The three SSC categories are:
 - Upper Respiratory symptoms: runny nose, stuffy nose, sneezing, sore throat, earache
 - Lower Respiratory symptoms: cough, shortness of breath, chest tightness, wheeze
 - Systemic symptoms: malaise, headache, muscle and/or joint ache, chilliness/feverishness
- Occurrence of RSV infection defined as two quantifiable RT-PCR measurements plus any clinical symptom of any severity.
- Total weight of mucus produced and tissue count.
- Safety and tolerability
 - Unsolicited adverse events (AEs) from informed consent form (ICF) signature until 28 days after vaccination, and from the entry into the Unit until 28 days after challenge.
 - Safety data including, but not limited to, physical examinations, vital signs, 12-lead electrocardiograms (ECGs) and clinical laboratory results (including biochemistry, hematology, and urinalysis).
 - Serious adverse events (SAEs) throughout the study (from signing the ICF to the end of the study, 6 months after vaccination).
 - Solicited local and systemic AEs for 7 days after vaccination.

Exploratory Endpoints

- AUC of the total clinical symptom score. The total clinical symptom score is a composite of 13 self-reported symptoms (on the SSC) divided into three categories (Upper Respiratory, Lower Respiratory, Systemic).
- The VL-AUC of RSV-A Memphis 37b, as determined by quantitative culture of RSV of nasal wash samples.
- Pre-F antibody in nasal wash samples measured by pre-F enzyme-linked immunosorbent assay (ELISA) normalized to a standard protein or antibody to account for variability of sample volume, dilution and concentration in nasal wash samples.
- Proportion of subjects with symptomatic RSV infection (RT-PCR or serology). Seroconversion is defined as a four-fold rise against the G and/or N protein by ELISA which would indicate a take of the virus inoculum to such extent that a systemic immunologic response against an antigen not in the vaccine was induced.

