Since preclinical models have suggested some level of protection by the vaccine against nasopharyngeal infection, the study includes a formal primary objective of lowering area under the curve of viral load (VL-AUC), despite the exploratory nature of this study. This VL-AUC has been found in previous studies to be the most sensitive and least variable parameter for efficacy measurement in this model. If the vaccine can prevent infection completely in some subjects, a powerful effect on the AUC would be seen since in those subjects the AUC would be 0. There are also a small number of secondary objectives related to reduction of symptoms

occurring at a specific time, reduction of overall mucous secretion and incidence of infection utilizing more severe or very mild symptoms as alternative definitions, coupled in both cases with two quantifiable RT-PCR measurements to confirm the symptoms are due to RSV.

The statistical approach to this exploratory study is to have an alpha of 20% to indicate a trend and 5% as a significant result for the primary endpoint. If positive results or a trend in the primary or secondary objectives are found, this would suggest that the challenge model may be a reasonable approach to examine vaccine efficacy and would provide evidence to perform more extensive studies. If this study fails its primary endpoint, and does not show any trends in the other endpoints, it would suggest that the human RSV challenge model is not an appropriate model to evaluate potential efficacy of RSV vaccines directed against more serious disease that has more of a lower respiratory component.

Therefore this study will serve as a pilot to explore the value of evaluating RSV vaccines in the human challenge model in RSV vaccine development, with the possibility that, if the model is appropriate, a trend toward efficacy with Ad26.RSV.preF could be detected.

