9.1.5. Viral Challenge Phase

9.1.5.1. Entry to the Quarantine Unit

Subjects will enter the quarantine Unit either one or two days before the viral challenge, to acclimatize and perform entry assessments. The following assessments can take place on either day: complete physical examination, including body weight, relevant medical information since vaccination, vital signs and spirometry, samples for clinical laboratory tests (including cardiac enzymes), ECG, blood samples for immunogenicity assessments, spirometry, and recording of any unsolicited AEs/SAEs and concomitant medications. Nasopharyngeal swabs and nasal wash samples will be collected to screen for respiratory virus and for RSV pre-F antibody assessment, respectively, and blood samples will be taken to determine sero-susceptibility for RSV for post-hoc reconfirmation (neutralization assay).

The SSC will be filled out by the subject and reviewed by the attending physician. Tissues for tissue counts and mucus weight will be distributed on Day -1. The first 24-hour collection will start on Day -1; tissue counts and mucus weights will be determined on Day 0.

A serum pregnancy test (β -hCG) will be performed for all female subjects. A urine drug screen, a urine cotinine test, and an alcohol breath test will be performed.

Throughout the challenge phase of the study from entry to the Unit until discharge, subjects will stay in individual isolation rooms to minimize cross-contamination between subjects.

Before challenge inoculation on Day 0, the subject's clinical status will be checked, including any available laboratory results or receipt of additional medical records.

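### The symptomatic-infection definitions can misclassify subjects: the Grade 2 criterion lacks an 'or higher', the SAP drops N from serology undeclared, and no definition has a symptom window

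*SAP*

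**What the plan says.** SAP 6.2 gives three definitions of symptomatic RSV infection.

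- **Conservative (secondary).** Two or more quantifiable RT-PCR results, plus either symptoms from two card categories, "regardless of grade and assessment timepoint", or "any Grade 2 symptom from any category". Protocol 11.4 has the same two limbs, and protocol 2.1.2 has the same Grade 2 wording.
- **Liberal, RT-PCR (secondary).** Two or more quantifiable RT-PCR results plus any card symptom of any severity.
- **Liberal, RT-PCR or serology (exploratory).** As above, but serology can replace RT-PCR. Serology is a "4-fold increase in G a or G b Elisa, 28 days after challenge".

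The grade scale is in the same SAP section: "The symptom scores will be translated into numerical values as follows", running from 0 to 4. Score 3 is described as "quite bothersome most or all the time and it stops me from participating in activities", and score 4 is worse. The sample card in protocol Attachment 3 is redacted, so the SAP is the only visible source for the scale.

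The protocol's serology rule (Synopsis and 2.1.2) reads "Seroconversion is defined as a four-fold rise against the G and/or N protein by ELISA".

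On Day -2 or -1, at entry to the Unit, "The SSC will be filled out by the subject and reviewed by the attending physician" (protocol 9.1.5.1). Cards are then completed three times daily until discharge.

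**The concern.** An endpoint definition has to say exactly who is a case, because someone will program it. Three places here do not.

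First, protocol 1.2 explains the paired definitions as "utilizing more severe or very mild symptoms as alternative definitions". The definition meant for more severe illness names Grade 2 alone, so it can miss Grades 3 and 4. Elsewhere the documents write thresholds out in full: at least Grade 1 for hemoglobin change (SAP 7.2), Grade 3 or 4 in the pausing rules (protocol 11.10), and above Grade 0 for card findings (protocol 9.2.4). A programmer following the text would code equality with 2.

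Second, the SAP's serology rule is narrower than the protocol's, and SAP Section 2, which is where changes are declared, mentions only the ECG tables and an RT-PCR sensitivity analysis. The rule also does not repeat which sample the rise is measured from.

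Third, no definition states a symptom window, so nothing excludes a pre-challenge card.

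These endpoints are not powered, but they do count. Protocol 1.2 would judge the challenge model unsuitable if the primary endpoint fails and the other endpoints show no trend. SAP 6.2.1 reports differences in proportions with confidence intervals and may use the definitions to split other efficacy summaries. SAP Section 9 may use them to group immune responses.

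**Working it through.** The documents give no power or expected rate for symptomatic infection, so there is no planned figure to reproduce. The check is to apply the rules literally to constructed subjects, then apply them again with three edits: Grade 2 or higher, symptoms only after inoculation, and G and/or N.

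| Constructed subject | Definition | As written | After edits |
|---|---|---|---|
| PCR-positive, upper respiratory only, Grade 1 then 3, never 2 | Conservative | non-case | case |
| PCR-positive, upper respiratory only, Grade 4 only | Conservative | non-case | case |
| PCR-positive, upper respiratory only, Grade 2 then 3 | Conservative | case | case |
| PCR-positive, Grade 1 headache on Day -1, Grade 1 upper respiratory after challenge | Conservative | case | non-case |
| PCR-positive, Grade 2 headache on Day -1 only | Conservative and both Liberal | case | non-case |
| PCR-positive, Grade 1 headache on Day -1 only | Both Liberal | case | non-case |
| PCR-negative, symptomatic after challenge, N rise 4.5-fold, G rise 2-fold | Liberal (RT-PCR or serology) | non-case | case |
| PCR-negative, symptomatic after challenge, G rise 4.5-fold, N rise 2-fold | Liberal (RT-PCR or serology) | case | case |

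The grade wording therefore affects the conservative definition only. The missing window affects all three. The N omission affects the exploratory definition only.

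**Size per subject.** With 22 challenged per arm (protocol 11.2), one reclassified subject is 1/22 = 0.045, or 4.5 percentage points of that arm.

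**Serology reference.** SAP 3.1 sets two baselines: the last assessment before vaccination for immunogenicity, and the last before challenge for efficacy. The endpoint sits in the efficacy section, and protocol 3.1 schedules blood one to two days before challenge. The pre-challenge sample is thus available and is the consistent choice. It is simply not named in the rule.

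**Direction of the window effect.** RT-PCR positivity is still required in the two secondary definitions, so a pre-challenge symptom can only promote a PCR-positive subject. Take 65% positivity on placebo (protocol 11.2) and an assumed 30% on vaccine.

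- If the share of positives counted as symptomatic rises from 70% to 80% in both arms (assumed), the difference goes from 0.65 × 0.70 − 0.30 × 0.70 = 24.5 points to 0.65 × 0.80 − 0.30 × 0.80 = 28 points. It widens.
- If placebo positives are already at 80% and only vaccine positives rise from 70% to 80%, it goes from 0.65 × 0.80 − 0.30 × 0.70 = 31 points to 28 points. It narrows.

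The direction depends on rates that the documents do not give.

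**The case against.** The best defence is that this is loose drafting with little practical effect. Much of that stands.

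- **Grade 2.** The wording matters only for a PCR-positive subject with symptoms in one category who reaches Grade 3 or 4 without ever recording Grade 2 on thrice-daily cards. Protocol 1.2 expects mild symptoms in this model, and such a subject still counts under both Liberal definitions. A reader might infer that the severe cases are generally lost. The documents do not support that.
- **Window.** A reader might infer that the SAP expressly counts pre-challenge symptoms. It does not. The timepoint phrase belongs to the two-category limb and may mean only that the two categories need not coincide. Acute illness within 7 days of admission and active respiratory infection also bar challenge (protocol 4.3). What remains is that no window is written, and a minor headache at entry need not bar challenge.
- **Serology baseline.** A reader might infer that the four-fold rise runs from the pre-vaccination sample, so that a natural infection before challenge would count as a take. SAP 3.1 gives efficacy a pre-challenge baseline, so that inference fails. The rule needs a clarifying phrase only.
- **N protein.** SAP 8.1 lists the G/N ELISA among assays that may be run if available, so there may be a practical reason for the omission. That would justify the change, but Section 2 would still have to record it.

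**Conclusion.** The point holds as a matter of definition. Two written rules misclassify if followed: the Grade 2 limb, against the protocol's stated purpose, and the serology criterion, against the protocol's own definition. The third, the missing symptom window, is an omission that leaves a choice open to whoever programs the endpoint.

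The size is 4.5 percentage points of an arm for each reclassified subject. The number of subjects cannot be derived. It is tempting to assume that 10–20% report a symptom at admission and conclude that 2.2 to 4.4 subjects per arm (22 × 0.10 to 22 × 0.20) are misclassified. That rate has no source in the documents, and the product counts everyone with an admission symptom. Requiring PCR positivity at 65% already cuts it to 1.4 to 2.9 on placebo, before the further condition that case status depends on that symptom. It is equally tempting to say that pre-challenge symptoms pull the arms together, but the arithmetic shows that the difference can widen or narrow.

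Only unpowered secondary and exploratory endpoints are affected. The primary VL-AUC test uses neither symptoms nor serology and is untouched.

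**What to change.** 1. **Severity limb.** In SAP 6.2 and protocol 2.1.2 and 11.4, replace the Grade 2 wording with *any symptom of Grade 2 or higher*. Conform the repeats in the protocol Synopsis, 2.1.1 and Attachment 2, and in SAP 1.1.
2. **Serology.** In SAP 6.2, restore *G and/or N*. If the N ELISA will not be run, record and justify the removal in SAP Section 2 instead. State that the four-fold rise is measured from the pre-challenge sample to 28 days after challenge, in line with the efficacy baseline in SAP 3.1.
3. **Window.** Add *recorded after inoculation and up to discharge* to all three definitions. This matches the period protocol 9.2.4 already uses when it attributes card findings to the challenge virus for adverse-event reporting.

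A further rule that a symptom must be absent from, or worse than on, the last pre-challenge card is not needed. It would add a new criterion and sit awkwardly with protocol 9.2.4, which presumes that every card finding above Grade 0 after challenge reflects the infection.

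The cost is a few lines of text, settled before treatment codes are released for the primary analysis. The protocol wording needs an amendment. Items 1 and 3 need no new data; item 2 needs the N ELISA only if N is kept.
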